The PROMISE Risk Tool was expressly developed to identify low-risk patients with stable chest pain who are unlikely to benefit from non-invasive testing, and for whom guideline-recommended medical management alone may be safe. Current guidelines recommend using a version of the Diamond and Forrester risk score for pretest likelihood of obstructive CAD, but multiple investigators have found that this tool grossly over estimates actual presence of disease^{5, 31, 32}. The consequence is an imprecise evaluation strategy for millions of patients, resulting in unhelpful testing of lower risk individuals. For a significant portion of these, a false positive functional testing leads them to have invasive cardiac catheterizations to rule out the disease they do not have. The Risk Tool developed using the PROMISE cohort employs 10 readily available clinical variables (such as tobacco usage, ethnicity/race, and age) and has been validated in the SCOT-HEART population^{33, 34}. This risk tool identifies patients with stable chest pain who have no coronary plaque or calcification by cCTA and no cardiac events over 2 years, and who therefore would be predicted to derive minimal or no value from noninvasive testing^{33, 34}. Testing whether this risk tool can be employed prospectively to safely and effectively risk stratify low risk patients into a strategy of guideline-recommended care with symptom and risk factor management and without diagnostic testing is one of the core secondary objectives of the PRECISE research program.

III.B. Rationale for the Current Study: A Precision Approach to Chest Pain Evaluation

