PRECISE will evaluate whether a precision evaluation strategy that combines contemporary risk stratification using the PROMISE Risk Tool with functional and anatomic non-invasive evaluation with cCTA with selective FFR_{CT} can improve outcomes over usual care in stable chest pain patients while safely deferring further testing in low-risk patients and reducing cost overall. While current guidelines recommend the non-invasive and invasive initial testing approaches for patients with stable chest pain³⁷, current practice is known to lead to high rates of ICA without obstructive CAD^{6, 40}. Further, although guidelines also recommend no testing in the lowest risk groups (pre-test probability of obstructive CAD <10 or 15%), currently available risk tools result in many clinicians appearing to ignore this recommendation: current patterns of care using available risk stratification tools results in testing populations with a prevalence of obstructive CAD of only 10-20%, and a prevalence of no coronary plaque of >25%^{4, 5}. The intervention in PRECISE will triage patients into two risk groups who will be assigned to receive either guideline-recommended medical management without planned testing or cCTA with selective FFR_{CT}. The PROMISE Risk Tool can identify low-risk patients with stable chest pain that would be expected to derive minimal value from noninvasive testing and is superior to either Framingham Risk Score or Diamond and Forrester assessments³³.

³⁴. cCTA with selective FFR_{CT} represents a combined functional and anatomic testing modality that can lower the frequency of finding no obstructive CAD at catheterization and thus reduce costs^{7,41}.

IV.F. Randomization Method

Participants who meet all inclusion criteria and none of the exclusion criteria will be randomized in a ratio of 1:1 within a clinical center to either a precision evaluation strategy or usual care using an interactive web or voice-based system (IXRS). Randomization will be stratified by intended first test (if randomized to usual care) and by classification as low vs. elevated risk by the minimal risk model. Participants with known non-obstructive plaque will be included in the elevated risk strata regardless of risk score. The randomization scheme within a clinical center will be carried out by the method of random permuted block design with variable block size.

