Participants randomized to the precision evaluation arm will be assigned a management approach based on their PROMISE Risk Score, a risk model based on pre-test clinical characteristics derived from the PROMISE trial and validated in SCOT-HEART³⁴ or the presence of known non- obstructive atherosclerosis. Participants will be assigned to either 1) guideline-recommended medical management without planned testing (low risk) or 2) cCTA with selective FFR_{CT} (elevated risk or those with known plaque, independent of the PROMISE Risk Tool assessment). Participants assigned to the strategy of guideline-recommended medical management without planned testing will be treated with risk-appropriate preventive care and symptom control (including therapeutic trials of anti-anginal medications). Participants and their providers will be provided informational materials demonstrating the safety of this strategy based on pre-test probabilities and the PROMISE Risk Score. Participants with intractable symptoms despite maximal medical management whose clinicians opt for further testing (crossovers) will undergo cCTA with selective FFR_{CT}.

Participants undergoing cCTA as the initial test (both assigned or crossover) should have FFR_{CT} analysis ordered if cCTA shows at least one 30-90% stenosis in epicardial vessels of 2mm diameter or greater. Image sets will be sent promptly to HeartFlow for analysis and results will be returned to sites in < 24 hours to enable rapid incorporation into clinical decision making.

V.D. Participant Follow-Up

Participants will be followed up at 45 (+/-14) days and at 6 and 12 months (+/- 30 days) after enrollment. For US participants, follow-up at 45 days and at 6 and 12 months will be done by phone interviews conducted by the DCRI Outcomes Call Center, unless not allowed by their enrolling site. For participants outside of the US, follow-up will be conducted by the site coordinators.

Activities to be conducted at each follow up contact are described below and in the Schedule of Events.

45 (+/-14) day follow-up visit (in-person, portions may be done by phone) At the 45-day follow-up visit, participants will be asked the following:

- Assessment if any MACE has occurred since enrollment

- CV Update: Review and documentation of any cardiovascular diagnostic test, cardiovascular procedure, or hospitalizations/clinic visits due to cardiovascular symptoms and complications since enrollment

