5.3 Subgroups of Intention-To-Treat and Per-Protocol

Four treatment comparisons will be made.

- Including only Intention-To-Treat participants from the low risk strata
- Including only Intention-To-Treat participants from the elevated risk or known atherosclerosis strata
- Including only Per-Protocol participants from the low risk strata
- Including only Per-Protocol participants from the elevated risk or known atherosclerosis strata

6. Participant Randomization and Enrollment

Once a participant has consented to participate in the trial, participant information will be entered in the database. If a patient is a screen failure, the data that have been collected up until this point for the patient for screening purposes will be entered into the eCRF in the EDC system. No additional information will be collected after this point for such a patient.

Participants who meet all inclusion criteria and none of the exclusion criteria will be randomized in a ratio of 1:1 within a clinical center to either of the following 2 groups using an IXRS.

Precision care - precision care strategy

Usual care- usual care strategy

Randomization will be stratified by intended first test assuming usual care (invasive vs. noninvasive) and by classification as low vs. elevated risk by the PROMISE risk model (see derivation below in Section 6.1). For testing purposes, participants with known non-obstructive coronary atherosclerosis or plaque will be assigned to the elevated risk strata regardless of risk score. The randomization scheme within a clinical center will be carried out by the method of random permuted block design. Participants will be randomized to either the usual care arm or the precision evaluation arm within 14 days of screening. The following tables summarizes the strata:

Summary of Strata

Strata	First Test	Risk
1	Non-Invasive	Low Risk
2	Non-Invasive	Elevated Risk or Known Atherosclerosis
3	Invasive	Low Risk
4	Invasive	Elevated Risk or Known Atherosclerosis

Enrollment in the randomization strata of intended first test being noninvasive (vs. invasive testing or direct to catheterization) will be capped at 90% of the sample size.

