For eligible participants, medical history data will be captured in the EDC. In addition, sites will need to specify the intended first test that would be performed if the participant is randomized to the usual care arm. The participant will then be randomized to either the usual care arm or the precision evaluation arm. Once randomization occurs, the participant is considered enrolled in the study. If randomized to the precision evaluation arm, participants will be further assigned to guideline-recommended care without immediately planned testing or cCTA with selective FFR_{CT}.

Participants randomized to the usual care arm will undergo either noninvasive stress testing (exercise electrocardiogram, stress nuclear imaging including PET, stress MR, or stress echocardiogram), or invasive catheterization as the first evaluation, with the specific modality chosen at the discretion of the participant's clinician. Performance of cCTA or a calcium score as the initial test is excluded in this arm and prohibited as a subsequent test for the first 45 days after randomization.

Participants randomized to the precision evaluation arm will be assigned an initial evaluation and management approach based on their PROMISE risk score, a risk model based on pre-test clinical characteristics derived from the PROMISE trial and validated in SCOT-HEART, and presence of known mild atherosclerosis. Participants will be assigned to either guideline-recommended medical management without planned testing (low risk) or cCTA with selective FFR_{CT} (elevated risk or known including atherosclerosis; known mild atherosclerosis is defined as any of the following: non-obstructive CAD, CAC 0-99 HU, or unquantified coronary calcium seen on chest CT). Participants assigned to the strategy of no immediately planned testing and their providers will be given informational materials demonstrating the safety of this strategy based on pre-test probabilities and the PROMISE risk score. Participants with intractable

symptoms despite maximal medical management whose clinicians opt for further testing (escalation of care) will undergo cCTA with selective FFR_{CT}.

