6.1 Risk Groups based on PROMISE Risk Score

To calculate the PROMISE risk score use the following table estimates based on the risk score paper (Fordyce, JAMA Cardiology 2017). The Promise Score is equal to $1/(1+\exp(\text{logit}))$.

Logit Equation= $\gamma_1 + \gamma_2 * \text{Age (Years)} + \gamma_3 * \text{Sex(female=1)} + \gamma_4 * \text{Caucasian/Non-Hispanic (no=1)} + \gamma_5 * \text{Tobacco(current or former=1)} + \gamma_6 * \text{Diabetes(yes=1)} + \gamma_7 * \text{Dyslipidemia(yes=1)} + \gamma_8 * \text{Family history of premature (<55 years)Coronary artery disease(yes=1)} + \gamma_9 * \text{hypertension(yes=1)} + \text{Symptoms unrelated to physical or mental stress (not related=1)} + \gamma_{11} * \text{Symptoms unrelated to physical or mental stress(unknown=1)} + \gamma_{12} * \text{HDL (mg/dL)}$

Logit Equation coefficients

		HDL is available	HDL is not available	
			Female	Male
Intercept	γ_1	-3.7524	-3.7524	-3.7524
Age (Years)	γ_2	0.0842	0.0842	0.0842
Sex (female=1)	γ_3	-1.0264	-1.0264	-1.0264
Caucasian/Non-Hispanic (no=1)	γ_4	-0.1422	-0.1422	-0.1422
Tobacco (current or former=1)	γ_5	0.5264	0.5264	0.5264
Diabetes (yes=1)	γ_6	0.3141	0.3141	0.3141
Dyslipidemia (yes=1)	γ_7	0.4122	0.4122	0.4122
Family history of premature (<55 years) Coronary artery disease (yes=1)	γ_8	0.3086	0.3086	0.3086
Hypertension (yes=1)	γ_9	0.4078	0.4078	0.4078

Symptoms unrelated to physical or mental stress (not related=1)	γ_{10}	0.3086	-0.3086	-0.3086
Symptoms unrelated to physical or mental stress (unknown=1)	γ_{11}	-0.195	-0.195	-0.195
HDL (mg/dL)	γ_{12}	-0.00559	-0.318682 HDL constant	-0.252855 HDL constant

Risk groups will be defined as the following:

- Low Risk: Promise Score >0.46
- Elevated Risk: Promise Score ≤ 0.46

Low Risk and Elevated Risk groups are defined using a cut point based on the top 10% of low risk of the PROMISE Risk Score in the PROMISE cohort. Thus, in PRECISE, Low Risk is defined as an absolute score >0.46 .

7. Sample Size and Power Calculations

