9.3.4 Sensitivity Analyses

9.3.4.1 Validation of the Cut Point for PROMISE Risk Score

The prognostic cut point used for the PROMISE risk score will be validated in light of the results of PRECISE. The calibration and discrimination of PROMISE cut points in the PRECISE participant population will be evaluated. Logistic regression model will be used estimate the area under the curve quantified by calculating c-index statistic and mean observed and predicted mean plot. The following lists the outcomes and populations to be evaluated:

- Scenario 1: PRECISE primary endpoint all three components for All Randomized Participants
- Scenario 2: PRECISE primary endpoint two components: Death/MI only for All Randomized Participants
- Scenario 3: Prognostic Value of Risk Score for No CAD + No Event for All Randomized Participants, Only Precision Care Arm Receiving CTA
- Scenario 4: Prognostic Value of Risk Score for Significant or Severe CAD for All Randomized Participants, Only Precision Care Arm Receiving CTA

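### Scenario 3 of the PROMISE score validation mixes in participants sent to CTA because of known atherosclerosis, so the score would appear to over-predict above the 0.46 cut

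*SAP*

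**What the plan says.** SAP 9.3.4.1 states that "The calibration and discrimination of PROMISE cut points in the PRECISE participant population will be evaluated". It names a c-index and a plot of observed against predicted means, both from a logistic regression. The population and outcome of Scenario 3 are given as "Prognostic Value of Risk Score for No CAD + No Event for All Randomized Participants, Only Precision Care Arm Receiving CTA". Figure 4.12.3.1 and Table 4.12.3.2 in SAP 10 use the same population. None of these places excludes known atherosclerosis.

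Four other provisions decide who is in that population:

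- The cut (SAP 6.1): "Low Risk: Promise Score >0.46". A high score therefore means low risk.
- The override (SAP 6): "participants with known non-obstructive coronary atherosclerosis or plaque will be assigned to the elevated risk strata regardless of risk score". Protocol IV.F says the same: "Participants with known non-obstructive plaque will be included in the elevated risk strata regardless of risk score". Protocol V.C assigns CTA to "elevated risk or those with known plaque, independent of the PROMISE Risk Tool assessment".
- The definition (SAP 6): "known mild atherosclerosis is defined as any of the following: non-obstructive CAD, CAC 0-99 HU, or unquantified coronary calcium seen on chest CT".
- The tool's target (Protocol III.A): it "identifies patients with stable chest pain who have no coronary plaque or calcification by cCTA and no cardiac events over 2 years".

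Low-risk participants without known atherosclerosis have no planned test (SAP 3 and 6). They reach CTA only on escalation of care.

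**The concern.** Above 0.46, the plan gives only two routes to CTA: escalation from the low-risk group, or known atherosclerosis. The second group is selected by a prior finding that largely settles the Scenario 3 outcome. Someone with documented plaque or coronary calcium already fails an outcome that requires neither, before the score is applied. Every such participant is sent to CTA, but only a minority of the other above-cut participants are, so the validation set over-samples failures exactly where the cut is being tested.

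The trial could then report that the score over-predicts minimal risk, or that the cut should move, when the pattern comes from who was scanned. Protocol III.A makes prospective testing of this tool a core secondary objective, so the result would be read as more than an incidental check. No efficacy comparison is affected.

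**Working it through.** The plan states no figure for this analysis, so there is none to reproduce. The check has four steps.

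**1. Direction.** The score is 1/(1 + exp(logit)) (SAP 6.1), and age, tobacco, diabetes, dyslipidaemia, family history and hypertension all raise the logit. A higher score is therefore a higher predicted probability of minimal risk. Adding people who fail the outcome above 0.46 pulls the observed rate below the predicted rate.

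**2. Planned size of the above-cut group without known atherosclerosis.** SAP 7 gives 1050 per arm, about 20% assigned to no testing, and about 30% of those escalating: 1050 × 0.20 × 0.30 = 63.

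**3. Mixture arithmetic.** Let K be the number with known atherosclerosis and a score above 0.46, q their rate of No CAD + No Event, and p the mean prediction above the cut. Then f = K/(K + 63) and the gap (predicted minus observed) is f × (p − q). The documents give none of K, q or p. Assume p = 0.55 and q = 0.10, so p − q = 0.45:

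- K = 5: f = 5/68 = 0.074, gap 3.3 points.
- K = 10: f = 10/73 = 0.137, gap 6.2 points.
- K = 20: f = 20/83 = 0.241, gap 10.8 points.

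With q anywhere from 0 to 0.30, the gap is 1.8–4.0 points at K = 5 and 6.0–13.3 points at K = 20.

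**4. Simulation.** Assume logit(score) is normal with mean −1 and SD 1, which puts 20% above 0.46, and draw the outcome from the score. The CTA set is everyone at or below 0.46, everyone with known atherosclerosis, and a random 30% of the rest above the cut. Known-atherosclerosis prevalence is assumed to be 5, 10 or 20%. Two models bracket the unknown relation between known disease and the score.

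- *Added cases.* The score is calibrated in people without known atherosclerosis. Known cases always fail, and their logit score is shifted by 0 or −0.3. Predicted above the cut is about 0.59. Observed is 0.51–0.53, 0.43–0.48 and 0.32–0.39 at the three prevalences, so the gaps run from about 6 points (0.59 − 0.53) to about 27 points (0.59 − 0.32).
- *Subset cases.* The score is calibrated in the whole population, and known cases are drawn from those with disease. Predicted/observed above the cut is 0.590/0.552, 0.590/0.520 and 0.586/0.463, so the gaps are about 4, 7 and 12 points. Below the cut calibration is intact (0.231/0.232 at 10%).

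Excluding known cases restores agreement above the cut in the added-cases model. In the subset model it overshoots. At 10% prevalence, predicted/observed becomes 0.594/0.629 above the cut and 0.233/0.260 below. At 20% it becomes 0.595/0.670 and 0.236/0.299.

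If the logistic model is refitted in PRECISE data, the gap shrinks but keeps its sign. At 10% prevalence in the added-cases model, predicted is 0.490 or 0.523 against observed 0.431 or 0.481, or 4–6 points instead of 11–16.

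**The case against.** The strongest reply is that the size depends on assumptions and the obvious remedy is not neutral. Much of this stands.

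- *Built-in gap.* The added-cases model is miscalibrated before any CTA selection. At 10% prevalence with no shift, the whole population above the cut has predicted 0.592 and observed 0.533. The subset model avoids this and gives smaller gaps, though in the same direction.
- *Exclusion can bias too.* Removing known cases removes only failures. If the tool was calibrated in a population that included known plaque, exclusion produces under-prediction. The documents do not say whether it was.
- *Undefined outcome.* The SAP does not define No CAD. The reading used here comes from the tool's target in Protocol III.A. If it meant no obstructive disease, the concern would weaken. The definition of known mild atherosclerosis also admits a calcium score of 0, so a reader might infer that every such participant has a predetermined outcome. The documents support only that most do.
- *Noise.* With 65–80 people above the cut, the standard error is near 6 points (√(0.55 × 0.45/65) = 0.062), so a 4-point gap would not stand out.
- *Escalators are selected.* Protocol V.E reserves escalation for accelerating symptoms or symptoms that persist despite treatment. Excluding known atherosclerosis leaves that selection in place.
- *Eligibility.* Protocol IV.A excludes any CAD proven by imaging, against inclusion criterion 3, Protocol IV.F and SAP 6. These passages must be reconciled, but the SAP plainly expects such participants.

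A reader might also extend the point to the other scenarios. The documents do not support that. Known non-obstructive plaque does not predetermine the primary endpoint (Scenario 1), death or MI (Scenario 2), or significant or severe CAD (Scenario 4). That the score did not assign these participants is no reason to drop them, because every participant is scored (Protocol IV.G), including those in usual care.

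**Conclusion.** The concern holds for Scenario 3. As written, the above-cut CTA group over-represents people who mostly cannot have the outcome, and the score would appear to over-predict there. The direction is the same in both models and with a refitted regression. The gap is about 4–12 points in the subset model and about 6–27 points in the added-cases model, for assumed prevalences of 5–20%. It is smaller with a refitted model or where known cases have a calcium score of 0. The actual size cannot be fixed from the documents, because they do not give the number of known-atherosclerosis participants above 0.46.

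The tool's two-year horizon against 12 months of follow-up here works the other way. At the event rate below 1% a year quoted in Protocol IX.B, it is worth about one point at most.

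A reader might infer that excluding these participants would by itself give an unbiased validation. It would not, because the escalators are selected and the tool's calibration population is unknown. That is why both versions are needed.

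**What to change.** In SAP 9.3.4.1 and outputs 4.12.3.1–4.12.3.2, for Scenario 3 only:

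- Make the main validation set precision-arm CTA recipients without known atherosclerosis at randomization, the group whose management the score decides.
- Report the full CTA set alongside as a sensitivity analysis.
- Above the cut, show known-atherosclerosis participants and escalators as separate rows.
- Define No CAD as the tool's own target, no plaque or calcification on cCTA. Also define No Event, and say whether predicted means come from the published score or a refitted model.

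Leave Scenarios 1, 2 and 4 unchanged.

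The cost is a few sentences and extra rows in two outputs. The stratum code merges elevated risk with known atherosclerosis, but atherosclerosis status is used for assignment and atherosclerosis history is listed for Table 2.2, so no new data collection appears necessary. The price is a smaller main set and possible under-prediction in it if the tool was calibrated in a population that included known plaque. Showing both versions makes that visible.

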9.3.4.2 Outcomes in Low and Elevated Risk groups

The following subgroup treatment/strategy comparisons will be conducted for the primary endpoint at 12 months as a forest plot with an interaction p-value. The primary endpoint along with the components analyses will be run for the the following populations:

- Including only Intention-To-Treat participants from the low risk strata
- Including only Intention-To-Treat participants from the elevated risk or known atherosclerosis strata

